13. ETHICS AND CONFIDENTIALITY

INFORMED CONSENT

It is the Investigator's responsibility to ensure written or electronic (if applicable) Informed Consent is obtained for each study subject in accordance with applicable regulations (e.g., ISO 14155-1, 21 CFR Part 50).

Subjects will be screened to determine their initial eligibility and interest in the study. Written or electronic (if applicable), study-specific Informed Consent will be obtained from each subject via the current IRB/EC approved Informed Consent Form (ICF) prior to the subject's participation in any study-related procedures, and prior to de-identified medical record or personal health information (PHI) being shared with any study representative. The subject's willingness to participate in the study will be documented in a study-specific Informed Consent Form, which will be signed and dated by the subject or their Legally Authorized Representative. The subjects will also be informed about study purpose, alternative treatments, potential risks/benefits of study participation, and the study assessment schedule.

The Investigator will keep the original consent form and a copy may be given to the subject. It will be explained to the subjects that they are free to refuse entry into the study and free to withdraw from the study at any time without prejudice to future treatment.

If, at any time during the study, new information becomes available or a protocol amendment requires an amendment to the ICF, active subjects may be asked to re-consent by signing an updated ICF. Copies of all signed ICFs will be maintained by the Investigator and will be made available to the Sponsor for monitoring purposes.

INSTITUTIONAL REVIEW BOARD (IRB) / ETHICS COMMITTEE (EC)

This study must be approved by an appropriate IRB/EC at each study site. Securing IRB/EC approval is the responsibility of the Investigator, as defined by GCP, ISO 14155-1 and FDA regulations (21 CFR Part 56), prior to starting the study.

The Sponsor must receive a copy of the IRB/EC approval letter (or equivalent documentation) for the study protocol and Informed Consent Form before the study can be started at that site.

The IRB/EC and Sponsor must approve any changes to the protocol, as well as a change of Principal Investigator. Documentation of IRB/EC approval must be provided to the Sponsor. Records of all study review and approval documents must be maintained by the Investigator in the Study File/ Regulatory Binder and are subject to inspection by the Sponsor (or designee) or regulatory authority during or after completion of the study.

The Investigator must notify the IRB/EC, as per their reporting guidelines, and the Sponsor when he or she deviates from the protocol. The Sponsor must be notified of all relevant action taken by the IRB/EC and must receive a copy of all study-related correspondence between the Investigator and the IRB/EC.

The IRB/EC must receive notification of study completion and a final report upon study completion or closure. A copy of these reports must be provided to the Sponsor. The Investigator must maintain an accurate and complete record of all submissions made to the IRB/EC.

STUDY SUBJECT CONFIDENTIALITY

The Investigator must ensure that the privacy of all subjects, including their personal identity and all personal health information. In CRFs and other documents or image material submitted to the Sponsor, subjects will not be identified by their names, but by an individual identification code (i.e., subject identification number).

Personal medical information may be reviewed for the purpose of verifying data recorded in the CRFs. A monitor or Sponsor designee may conduct source-document verification on behalf of the Sponsor, the quality assurance unit, or regulatory authorities. Personal medical information will always be treated, also when sent abroad, as confidential and handled in compliance with the Health Insurance Portability and Accountability Act (HIPAA) and General Data Protection Regulation (GDPR).

INDEPENDENT IMAGE REVIEW AND IMAGE TRANSFER

An independent reviewer may be utilized in the study, at the Sponsor's discretion. The independent reviewer will evaluate selected CT and Echocardiography images collected at baseline, 24 hours, and any unscheduled visits (if collected).

De-identified, electronic echocardiograms and CT images will be sent via secure electronic transfer to a secured imaging repository per US FDA/EU GDPR regulations. Where an electronic submission is not possible, de-identified images will be sent by other secure means per US FDA/EU GDPR regulations. Copies of images will be securely stored for a minimum of 10 years post study completion or 10 years after the last FlowTriever system or CDT system has been placed on the market (whichever is longer).

INVESTIGATOR RESPONSIBILITIES

Investigator responsibilities include, but are not limited to, the following:

- Conducting the study in accordance with this investigational plan, signed agreement, GCP, and applicable regulations protecting the rights and safety of study subjects
- Ensuring that informed consent is obtained for each study subject in accordance with GCP and applicable regulations (e.g., ISO 14155-1, 21 CFR Part 50)
- Ensuring that IRB/EC approval is secured prior to starting the study and ensuring continuing review and approval as required throughout the investigation
- Ensuring all associates, colleagues, and employees assisting in the conduct of the study are informed about their obligations, are adequately qualified and trained, and meet their commitments
- Maintaining adequate and accurate records and ensuring those records are available for inspection at any time
- Ensuring that conducting the study does not give rise to a conflict of interest (financial disclosure is required)

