2.6. Secondary Endpoints

The secondary endpoints of the study will assess safety, effectiveness, and utility measures, as follows:

- Composite clinical endpoint constructed as a win ratio hierarchy of the following four components, assessed at hospital discharge or at 7 days after the index procedure, whichever is sooner:
 - All-cause mortality, or
 - Intracranial hemorrhage (ICH), or
 - Major bleeding per ISTH³ definition, or
 - Clinical deterioration defined by hemodynamic or respiratory worsening, and/or escalation to a bailout therapy
- Individual components of the win ratio composite endpoint, assessed at hospital discharge or at 7 days after the index procedure, whichever is sooner:
 - All-cause mortality
 - Intracranial hemorrhage (ICH)
 - Major bleeding per ISTH³ definition
 - Clinical deterioration defined by hemodynamic or respiratory worsening, and/or escalation to a bailout therapy
 - ICU admission and post index procedure ICU length of stay
- All-cause mortality within 30 days from index procedure
- PE-related and all-cause readmission within 30 days from index procedure
- Device and drug-related serious adverse events through the 30 day visit
- Clinically Relevant Non-Major (CRNM) and Minor bleeding events through hospital discharge or at 7 days after the index procedure, whichever is sooner
- Change in core-lab-adjudicated right-ventricular/left-ventricular (RV/LV) ratio from baseline to 24 hour visit, as measured by echocardiography or CT
- mMRC Dyspnea score at 24 hour visit and 30 day visit
- Length of post-index-procedure hospital stay (to a maximum of 30 days)
- Disease-specific and general health-related quality of life at the 30 day visit (PEmb-QoL and EQ-5D-5L)

PROPRIETARY AND CONFIDENTIAL

The information contained in this document is the sole property of Inari Medical

	PEERLESS Study: Statistical Analysis Plan	Version 5.0 March 22, 2024 Page 14 of 25
---	--	--

3. Analysis Populations

The analysis populations are defined as follows.

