5.4.12. Change in RV/LV Ratio

Change in right-ventricular/left-ventricular (RV/LV) ratio from baseline to 24 hour visit, as measured by echocardiography or CT, will be analyzed as with the following null and alternative hypotheses:

$$H_0: \mu_{RF} \leq \mu_{RC} \text{ versus } H_A: \mu_{RF} > \mu_{RC}$$

where μ_{RF} represents the mean reduction in the RV/LV ratio treated from baseline to 24 hour visit in the FlowTriever System group, and μ_{RC} represents the mean reduction in the RV/LV ratio treated from baseline to 24 hour visit in the CDT group. The hypothesis will be tested using a Wilcoxon Rank Sum test.

5.4.13. mMRC Dyspnea Score at 24 Hour Visit

The mMRC Dyspnea score at 24 hour visit will be analyzed as with the following null and alternative hypotheses:

$$H_0: p_{mD24hF0} \leq p_{mD24hC0} \text{ and } p_{mD24hF1} \geq p_{mD24hC1} \text{ and } p_{mD24hF2} \geq p_{mD24hC2} \text{ and } p_{mD24hF3} \geq p_{mD24hC3} \text{ and } p_{mD24hF4} \geq p_{mD24hC4}$$

versus

$$H_A: p_{mD24hF0} > p_{mD24hC0} \text{ or } p_{mD24hF1} < p_{mD24hC1} \text{ or } p_{mD24hF2} < p_{mD24hC2} \text{ or } p_{mD24hF3} < p_{mD24hC3} \text{ or } p_{mD24hF4} < p_{mD24hC4}$$

PROPRIETARY AND CONFIDENTIAL

	PEERLESS Study: Statistical Analysis Plan	Version 5.0 March 22, 2024 Page 22 of 25
---	--	--

where $p_{mD24hFz}$ represents the proportion of subjects with mMRC Dyspnea Score equal to z at 24 hour visit in the FlowTriever System group, where $z = 0, 1, 2, 3$, and 4 ; and, $p_{mD24hCz}$ represents the proportion of subjects with mMRC Dyspnea Score equal to z at 24 hour visit in the CDT group, where $z = 0, 1, 2, 3$, and 4 . The hypothesis will be tested using a Fisher's exact test.

5.4.14. mMRC Dyspnea Score at 30 Day Visit

The mMRC Dyspnea score at 30 day visit will be analyzed as with the following null and alternative hypotheses:

$H_0: p_{mD30dF0} \leq p_{mD30dC0}$ and $p_{mD30dF1} \geq p_{mD30dC1}$ and $p_{mD30dF2} \geq p_{mD30dC2}$ and $p_{mD30dF3} \geq p_{mD30dC3}$ and $p_{mD30dF4} \geq p_{mD30dC4}$

versus

$H_A: p_{mD30dF0} > p_{mD30dC0}$ or $p_{mD30dF1} < p_{mD30dC1}$ or $p_{mD30dF2} < p_{mD30dC2}$ or $p_{mD30dF3} < p_{mD30dC3}$ or $p_{mD30dF4} < p_{mD30dC4}$

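### The SAP defines the RV/LV endpoint on core-lab values, but the protocol leaves independent reading optional and limited to selected images, and neither document masks the reader

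*Protocol*

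**What the plan says.** **Endpoint definition.** SAP 2.6 lists "Change in core-lab-adjudicated right-ventricular/left-ventricular (RV/LV) ratio from baseline to 24 hour visit, as measured by echocardiography or CT". The protocol's own endpoint list (section 5, Secondary Endpoints) names no reader.

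**Endpoint as tested.** SAP 5.4.12, which sets the hypotheses and the Wilcoxon rank-sum test, begins "Change in right-ventricular/left-ventricular (RV/LV) ratio from baseline to 24 hour visit, as measured by echocardiography or CT, will be analyzed". The core-lab qualifier is absent there, and also in the list of non-safety endpoints in SAP 5.6.

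**Who reads the images.** Protocol section 13, Independent Image Review and Image Transfer, says "An independent reviewer may be utilized in the study, at the Sponsor's discretion", and then "The independent reviewer will evaluate selected CT and Echocardiography images collected at baseline, 24 hours, and any unscheduled visits". It does not say who selects, by what rule or when. The same section provides for transfer: "De-identified, electronic echocardiograms and CT images will be sent via secure electronic transfer to a secured imaging repository per US FDA/EU GDPR regulations".

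**Setting.** SAP section 2 describes the trial as open-label. SAP section 4 makes complete-case analysis the main analysis, with multiple imputation as a sensitivity analysis. SAP 5.6 tests RV/LV within a non-safety family held at one-sided 0.025, divided by an effective number of independent tests.

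**The concern.** The SAP's definition needs a core-lab reading for every pair of images, and the protocol does not promise one. If only core-lab values count, a subject whose images were not chosen for reading has no endpoint value and drops out of the complete-case analysis. Because selection can take place after treatment in an open-label trial and no rule governs it, the pairs that remain need not be a random subset of either arm. If the analyst instead follows SAP 5.4.12 and the protocol endpoint list literally, readings by site staff who know the arm would satisfy the wording.

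RV/LV change is the only imaging endpoint listed, it is hypothesis-tested, and it is a measurement that involves judgement by the reader. Masked and complete reading is the usual protection, and neither document requires it.

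**Working it through.** **1. Do the texts agree?**

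| Place | Core-lab values required? | All pairs read? | Reader masked? |
|---|---|---|---|
| Protocol 5, Secondary Endpoints | Not stated | Not stated | Not stated |
| Protocol 13, Independent Image Review | Optional | No, selected images | Not stated |
| SAP 2.6 | Yes | Implied only | Not stated |
| SAP 5.4.12 and 5.6 | Not stated | Not stated | Not stated |

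**2. Does another provision close the gap?**
- The Clinical Events Committee (Protocol 9) adjudicates safety-related endpoints, and its list does not include RV/LV.
- Data masking (SAP 6) protects the biostatistics and programming team, not the image readers.
- De-identification (Protocol 13) removes the subject's identity. Nothing says that it hides arm or time order.
- Transfer to a repository makes a full central read feasible but does not require it.
- Multiple imputation (SAP 4) is a sensitivity analysis, and no rule deals specifically with unread images.

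**3. How large could it be?** The documents give no power or error figure for RV/LV, so there is none to reproduce. What follows is illustration.

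Inputs from the documents:
- SD of RV/LV change 0.30, from the single-arm FlowTriever study (Protocol 3, FLARE Study Results), and 0.42, from the conventional CDT arm of the randomised comparison with ultrasound-assisted thrombolysis (Protocol 3). Both are 48-hour values, used here for a 24-hour endpoint.
- Up to 550 randomised 1:1, so 550/2 = 275 per arm.
- Non-safety tests in SAP 5.6: ICU admission and stay, RV/LV, mMRC at 24 hours, mMRC at 30 days, post-procedure hospital stay, PEmb-QoL and EQ-5D-5L, seven in all. The divisor lies between 1 and 7, so the one-sided level lies between 0.025 (critical value 1.960) and 0.025/7 = 0.00357 (critical value 2.690).

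Assumptions found in neither document: 250 readable pairs per arm, a differential reading shift d = 0.05 favouring FlowTriever, and a true difference of 0.10 for the power figures.

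*(a) All images site-read, no true difference.* With the normal approximation to the rank-sum test, z = (d/SD) × √(n/2), and the rejection rate is 1 − Φ(critical value − z).
- SD 0.30: z = (0.05/0.30) × √125 = 1.863. The rate is 1 − Φ(0.097) = 46% at 0.025, and 1 − Φ(0.827) = 20% at 0.025/7.
- SD 0.42: z = (0.05/0.42) × √125 = 1.331. The rate is 1 − Φ(0.629) = 26% at 0.025, and 1 − Φ(1.359) = 9% at 0.025/7.

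*(b) Only half the pairs read at the core lab.* Two effects need separating.
- Loss of information, even if selection is harmless. For a true difference of 0.10, reducing 275 per arm to 137.5 lowers power at 0.025 from 97% to 79% (SD 0.30) or from 80% to 51% (SD 0.42). At 0.025/7 it falls from 89% to 53%, or from 54% to 24%.
- Selection that differs by arm. If the chosen pairs differed between arms by 0.05 in mean change although the full arms did not, the formula in (a) applies with n = 125. For SD 0.30, z = (0.05/0.30) × √62.5 = 1.318, giving 26% at 0.025 and about 8.5% at 0.025/7. For SD 0.42, z = 0.941, giving 15% and 4%.

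**The case against.** The strongest reply is that the documents can be reconciled. The protocol permits an independent reviewer, SAP 2.6 exercises that option by naming core-lab values, and SAP 5.4.12 and 5.6 merely repeat the endpoint in short form. On that reading no site-read analysis is planned, and the repository already holds what a full central read would need.

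Much of this stands. A reader might infer that the plan prescribes a site-read endpoint. It does not: site reading would contradict SAP 2.6, and no section names site readings as the source. A reader might also infer that the sponsor picks the images. The sponsor's discretion attaches to using a reviewer at all, and the next sentence leaves the selector unnamed. Nor do the documents show that any biased selection or reading took place.

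The reply does not deal with the restriction to selected images. Reading SAP 2.6 as decisive settles whose values count, but not whether every pair gets one, nor what the reader knows. With complete-case analysis, that restriction determines who is analysed.

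**Conclusion.** The point holds as a gap between the two documents on a hypothesis-tested secondary endpoint. The text permits an RV/LV test on a non-randomly chosen subset of pairs, read by someone who may know the arm and the time order. It affects one of seven non-safety secondary tests. The primary hierarchy contains no imaging component, and its first four components are adjudicated by the Clinical Events Committee.

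The error rates above show sensitivity and are not an estimate. They depend on an assumed 0.05 shift, assumed numbers of pairs and 48-hour SDs, and they fall as the multiplicity divisor rises from 1 towards 7. A reader might take the 46% as the trial's error rate. It is the top of a range, at the smaller SD and the unadjusted level, for a site-read analysis that SAP 2.6 does not intend. Label: cheap improvement.

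**What to change.** **Protocol 13.** Replace the optional and selected-image wording with: *all baseline and 24-hour CT/echo images of RCT subjects will be read by the core lab without knowledge of arm, site or time order, as far as the images allow.*

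**SAP 5.4.12 and 5.6.** Carry over the core-lab-adjudicated qualifier from SAP 2.6. State that only core-lab values are tested and that site readings are supportive. Report the number of unread or unreadable pairs by arm, with reasons.

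**Cost.** Wording changes in both documents, and some added reading time at the core lab that the SAP's endpoint definition already presupposes. No new reader role is needed. Masking will be incomplete in some cases, because a CDT catheter still visible at 24 hours may reveal the arm.

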14. ELECTRONIC DATA

Electronic data will only be accessible to authorized personnel with a unique user identifier and password for the EDC. Passwords will be set to expire periodically. Access to electronic study data will be provided to research personnel upon completion of training. Read and write access will be provided to investigational sites but only for information and subject data at their site. The Sponsor and designee will have read-only access and can post queries for potential data-related discrepancies.

15. PUBLICATION OF TRIAL RESULTS

A description of the clinical trial results will be available on <http://www.ClinicalTrials.gov> (Ref: NTC05111613), within 1 year after the completion of the clinical trial. This web site will not include any identifiable subject information but will include a summary of the results.

The sponsor will also seek publication of the trial primary and secondary objectives in international peer-reviewed journals.

16. FUTURE USE OF DATA FOR RESEARCH PURPOSES

The subject clinical data and echocardiography images collected in the PEERLESS Study could play an important role in answering clinical questions in the future and could therefore be used in clinical investigations that have not been defined yet (= further use).

For research projects with not yet defined research questions we will collect the consent for “further use of data” and only data from patients who agreed to the “further use of data” will be considered.

17. TERMS AND DEFINITIONS

Primary Endpoint Definitions	
Index Procedure	The index procedure begins when access for treatment is obtained. The index procedure is considered complete when the subject leaves the procedure room.
Intracranial Hemorrhage	Intracranial hemorrhage (ICH) is defined as ANY bleeding involving the brain parenchyma, ventricular system, or subarachnoid, subdural, or epidural regions, as identified by CT scan or MRI, regardless of symptoms.
Major Bleeding	ISTH Major Bleeding ⁴ in non-surgical subjects: 
• Fatal bleeding; and/or• Symptomatic bleeding in a critical area or organ, such as intracranial, intraspinal, intraocular, retroperitoneal, intraarticular or pericardial, or intramuscular with compartment syndrome; and/or• Bleeding causing a fall in hemoglobin level of 2 g/dL (1.24 mmol/L) or more or leading to transfusion of two or more units of whole blood or red cells.
Clinical Deterioration	Clinical deterioration is defined as documented objective hemodynamic or respiratory worsening that is new (i.e. not present at the time of enrollment). Clinical deterioration is when one or more of the following is definitively documented , with relation to both the severity and the duration of the event: 
• Hypotension with systolic blood pressure <90 mm Hg lasting at least 30 minutes, unresponsive to fluid resuscitation, and requiring the addition of or increased dose of vasoressors• Fall in systolic blood pressure by 40 mm Hg or more, lasting at least 30 minutes, and accompanied end-organ hypoperfusion (such as oliguria, mental status changes, ischemic extremities)• Cardiac arrest requiring cardiopulmonary resuscitation• Bradycardia lasting more than 10 minutes, accompanied by hypotension, and requiring pharmacologic intervention or insertion of a pacemaker

	
• Ventricular tachycardia or fibrillation requiring pharmacologic intervention or defibrillation• Requirement for an increase in fraction of inspired oxygen requirements 0.20 or greater, lasting longer than 30 minutes (e.g. from 0.21 to 0.41)• Need for intubation in a previously non-intubated subject, or unplanned use of extracorporeal membrane oxygenation (ECMO) 
Note that transient fluctuations in hemodynamic and/or respiratory function may be common during thrombectomy and thrombolysis procedures, and events not meeting both severity and duration requirements are not considered meeting the definition of Clinical Deterioration. Such changes may resolve spontaneously upon continuation of an existing treatment plan, and as such are unremarkable. Vagal episodes are also, in themselves, not considered Clinical Deterioration. Shorter term changes in hemodynamic or respiratory function, when accompanied by an unplanned escalation of therapeutic measures under the primary clinician's judgement to avoid overt deterioration, may be considered Bailout Therapy. Any such escalations of therapy will be documented in detail and adjudicated by a Clinical Events Committee (CEC).

Bailout	
Bailout therapy is an unplanned escalation of therapeutic measures, taken when the patient's condition has not improved or is not improving according to expectations. Potential Bailout Therapy events will be adjudicated by a Clinical Events Committee, including when any of the following occur:
 
• Unplanned use of additional mechanical, pharmacomechanical, pharmacologic catheter-based therapies, or systemic thrombolytics, or changing from the assigned treatment strategy, after initial treatment strategy as assigned was initiated.
○ If catheter-directed thrombolysis (CDT) was the assigned treatment strategy and emergent/clinically driven systemic thrombolytic administration (e.g. ≥ 10 mg tPA) was required after CDT was initiated, this would be considered a bailout.
■ If the length of thrombolytic administration is simply extended and is not emergent or clinically driven, this would not qualify as a bailout.○ If mechanical thrombectomy was the assigned treatment strategy, low-dose catheter-directed adjunctive thrombolytic therapy (less than 10 mg tPA) that is administered intra-procedurally or post-procedurally will be strongly discouraged but not considered a bailout• Surgical thrombectomy 
Before escalating to a Bailout Therapy, physicians are encouraged to consider the patient's condition and identify one or more reasons from the

	
following list to justify the need for Bailout Therapy. These reason(s) will be documented in the study case report forms (CRFs).
 
• Persistent elevated respiratory rate• Ongoing or increased requirement for supplemental oxygen• Persistent or new-onset tachycardia• Sustained or sudden bradycardia• Sudden or persistent hypotension, not associated with a vagal episode, or signs of end-organ hypoperfusion• Hemodynamic worsening or lack of hemodynamic improvement• Lack of improved lung perfusion, or inadequate clot resolution• New-onset, persistent, or worsening symptoms of PE 
Any unplanned escalation of therapy adjudicated by the CEC to not meet clinical definitions for Bailout Therapies will be considered a protocol deviation.

ICU Admission/ICU Length of Stay	
ICU Admission will be defined as admission or transfer to an Intensive Care Unit (ICU), Critical Care Unit (CCU), or similar high-acuity floor, collectively referred to as "ICU." For the purpose of the endpoint assessment, ICU Admission is met under the following conditions:
 
• Orders are entered for Subject to be admitted or transferred to the ICU after the end of the Index Procedure and before hospital discharge from the index hospitalization, up to a maximum of 7 days from the end of the Index Procedure, or• Subject had been in the ICU leading up to the Index Procedure, with plans to return to the ICU immediately after the end of the Index Procedure, with or without a transfer to a PACU, recovery room, or similar temporary step-down unit according to local standard. 
ICU Length of Stay (LOS) is the total number of hours a subject is medically required to be in the ICU, measured from the end of the Index Procedure or the time of ICU Admission, whichever is later, until the time of an order to discharge the subject from the ICU or transfer the subject to a standard or lower-acuity unit. If a subject remains physically located in the ICU due to hospital bed availability, transport delays, or other non-medical reasons instead of a need for high acuity of care, the time of the order for discharge or transfer, rather than the actual time a subject physically leaves the ICU, is used for assessing ICU LOS.
 
For subjects getting discharged from or transferred off the ICU and returning again during the index hospitalization, up to a maximum of 7 days after the Index Procedure, the total hours of all ICU admissions or transfers during that period (i.e., after the Index Procedure and until hospital discharge up to a maximum of 7 days) are used for assessing ICU LOS.

	
Subjects who had been in the ICU leading up to the Index Procedure, but not returning to the ICU after the end of the Index Procedure, are not considered to have had an ICU Admission per the endpoint definition.
 
For the win ratio primary endpoint, ICU admission and ICU LOS are characterized hierarchically as follows:
 
1. No ICU Admission2. ICU Admission, lasting between 0 – 24 hours3. ICU Admission, lasting longer than 24 hours
--	--

Additional Safety Definitions	
Adverse Device Effect (ADE)	
An Adverse Device Effect (ADE) is an AE related to the use of an investigational medical device.
 
NOTE 1: This definition includes AEs resulting from insufficient or inadequate instructions for use, deployment, implantation, installation, or operation, or any malfunction of the investigational medical device.
 
NOTE 2: This definition includes any event resulting from an error use or from intentional misuse of the investigational medical device.
 
NOTE 3: This includes 'comparator' if the comparator is a medical device. (ISO 14155:2020, 3.1)

Adverse event (AE)	
An Adverse Event (AE) is an untoward medical occurrence, unintended disease or injury, or untoward clinical signs (including abnormal laboratory findings) in subjects, users or other persons, whether or not related to the investigational* medical device and whether anticipated or unanticipated (ISO 14155:2020, 3.2).
 
*NOTE 1: All devices used in this study are commercially available and, therefore, not considered investigational.
 
NOTE 2: This adverse event definition includes events related to the procedures involved.

CRNM	
Clinically Relevant Non-Major (bleeding): Any sign or symptom of hemorrhage (e.g., more bleeding than would be expected for a clinical circumstance, including bleeding found by imaging alone) that does not fit the criteria for the ISTH definition of major bleeding⁴ but does meet at least one of the following criteria:
 
i. requiring medical intervention by a healthcare professionalii. leading to hospitalization or increased level of careiii. prompting a face to face (i.e., not just a telephone or electronic communication) evaluation

Device Deficiency (DD)	
A Device Deficiency (DD) is the inadequacy of a medical device with respect to its identity, quality, durability, reliability, usability, safety or performance.
 
NOTE 1: DD include malfunctions, use errors and inadequacy in the information supplied by the manufacturer including labeling.
 
NOTE 2: This definition includes device deficiencies related to the investigational medical device or the comparator. (ISO 14155:2020, 3.19)

Device-related event	The event is directly related to the FlowTriever System or CDT system, as defined by its intended use. AEs will be considered unrelated to the device if the complication could have occurred if the device functioned entirely within its specifications.
Drug-related event	Event is attributable to thrombolytic or anticoagulant therapy. These events may occur from inadequate (thrombosis) or excessive therapy (bleeding). A drug-related AE cannot also be classified as device related, but many will be classified as procedure-related, since the drug may be part and parcel of the index procedure.
Minor bleeding	Any bleeding not classified as Major Bleeding or Clinically Relevant Non-Major, by ISTH definitions
Procedure-related event	Procedure-related events include all AEs that occur at any time of subject participation that was directly related to the procedure. The exception to this rule is an event that is device-related; such events should not also be classified as procedure-related.
Serious Adverse Device Effect (SADE)	A Serious Adverse Device Effect (SADE) is an adverse device effect that has resulted in any of the consequences characteristic of a serious adverse event. (ISO 14155:2020, 3.44)
Serious Adverse Event (SAE)	A Serious Adverse Event (SAE) is an adverse event that led to any of the following: 
a) death,b) serious deterioration in the health of the subject, users or other persons as defined by one or more of the following:
1) a life-threatening illness or injury, or2) a permanent impairment of a body structure or a body function, including chronic disease, or3) in-patient or prolonged hospitalization, or4) medical or surgical intervention to prevent life-threatening illness or injury or permanent impairment to a body structure or a body function,

	
5) fetal distress, fetal death or a congenital abnormality or birth defect including physical or mental impairment
 
NOTE 1: Planned hospitalization for a pre-existing condition, or a procedure required by the CIP, without serious deterioration in health, is not considered an SAE. (ISO 14155:2020, 3.45)

Unanticipated/Anticipated Serious Adverse Device Effect (USADE/ASADE)	
A USADE is a serious adverse device effect which by its nature, incidence, severity or outcome has not been identified in the current risk assessment.
 
An ASADE is an anticipated serious adverse device effect which by its nature, incidence, severity or outcome has been identified in the risk assessment. (ISO 14155:2020, 3.51)

Unanticipated Adverse Device Effect (UADE)	
An unanticipated adverse device effect (UADE) is any serious adverse effect on health or safety or any life-threatening problem or death caused by, or associated with, a device, if that effect, problem, or death, was not previously identified in a nature, severity, or degree of incidence in the investigational plan or application (including a supplementary plan or application), or any other unanticipated serious problem associated with a device that relates to the rights, safety, or welfare of subjects. (21 CFR 812.3(s))

Other Definitions	
Asymptomatic PE	Pulmonary embolism detected on an imaging study in a subject without clinical symptoms.
CTED/Post PE Syndrome	Chronic thromboembolic Disease: Per 2019 ESC Guidelines, ¹ some subjects may present with normal pulmonary hemodynamics at rest despite symptomatic disease. If other causes of exercise limitation are excluded, these subjects are considered as having chronic thromboembolic disease (CTED). From Respiratory medicine journal on PE, CTED is characterized by similar symptoms and imaging findings to CTEPH but without pulmonary hypertension at rest.
CTEPH	Chronic thromboembolic pulmonary hypertension: Per 2019 ESC Guidelines, ¹ CTEPH is a disease caused by the persistent obstruction of pulmonary arteries by organized thrombi, leading to flow redistribution and secondary remodeling of the pulmonary microvascular bed. The diagnosis of CTEPH is based on findings obtained after at least 3 months of effective anticoagulation, to distinguish this condition from acute PE. The diagnosis requires a mean PAP of ≥ 25 mmHg along with a pulmonary arterial wedge pressure of ≤ 15 mmHg, documented at right heart catheterization in a subject with mismatched perfusion defects on V/Q lung scan.
High-Risk PE	Per ESC guidelines 2019 ¹ : High-Risk PE determined by hemodynamic instability, PESI III-V or sPESI ≥ 1 , RV Dysfunction, and Elevated cardiac troponins. Note definition of hemodynamic instability, which delineates acute high-risk pulmonary embolism (one of the following clinical manifestations at presentation). 1. Cardiac Arrest: Need for cardiopulmonary resuscitation, 2. Obstructive Shock: Systolic BP < 90 mmHg or vasopressors required to achieve a BP ≥ 90 mmHg despite adequate filling status AND end-organ hypoperfusion (altered mental status; cold, clammy skin; oliguria/anuria; increased serum

	lactate), OR 3. Persistent Hypotension: Systolic BP < 90 mmHg or systolic BP drop \geq 40 mmHg, lasting longer than 15 min and not caused by new-onset arrhythmia, hypovolemia, or sepsis
Intermediate-High-Risk PE	Per ESC guidelines 2019 ¹ : Intermediate-High-Risk PE determined by no hemodynamic instability, PESI III-V or sPESI \geq 1, RV Dysfunction, and Elevated cardiac troponins
Intermediate-Low-Risk PE	Per ESC guidelines 2019 ¹ : Intermediate-Low-Risk PE determined by no hemodynamic instability, PESI III-V or sPESI \geq 1, and 1 or none of the following: RV Dysfunction; Elevated cardiac troponins.
Patient/Subject	Participants in the study.
Product Complaint:	Any written, electronic or oral communication that alleges deficiencies related to the identity, quality, durability, reliability, safety, effectiveness or performance of a medical device that has been placed on the market.
Recurrent PE	Symptomatic worsening from baseline of the embolism that was successfully treated with the index procedure with documentation of a change on CTPA or other suitable imaging modality.
Symptomatic PE	Clinical pulmonary embolism symptoms and/or signs such as chest pain, dyspnea, hemoptysis, palpitations, or tachycardia.

